3.3.2.2. If interested they will be provided information about the study and will be allowed to proceed to the telephone interview. These techniques have been used successfully in previous VABHCS studies of yoga interventions.(59) The VABHCS Institutional Review Board (IRB) will pre- approve all forms of advertisement. Current VA policy does not allow email communications as part of the recruitment procedures. Sample size calculations, based on power analyses, require the following number of completers equally divided between the yoga and walking groups to test the hypotheses for each dependent variable: **n=70** completers to test Aim 1: Depressive Symptoms and Mood Scale; **n=56** to test Aim 2: GABA changes; and **n=68** to test Aim 3: RSA changes [D.20]. To meet the criteria for each Aim/Dependent Variable n=70 subjects will complete the intervention with n=56 having usable MRS data. Using data from Study 4, with consideration of changes in inclusion and exclusion criteria and research setting, the following recruitment schedule will be required during a 5-year study period, which will include over 4 years of recruitment and treatment. The required total recruitment and annual requirements at each stage are as follows: telephone screen=420 total or 105/year; screening interview=173 total or 43/year; randomization=100 total or 25/year; and completers=68 total or 18/year.

3.3.2.3. Participation in Non-Assigned Group: A Retention Plan: Prior to randomization, subjects will be asked their group of choice (i.e., yoga or walking), as not being assigned to a group of choice could influence dropout rate. In order to retain subjects not assigned to their choice, subjects will be allowed to participate in the group they are not assigned to for 16 sessions or 8 weeks (i.e., the second intervention), whichever comes first, if they complete their randomized intervention and 14 week follow up phone call. Retention in the randomized intervention is given priority over contamination of the 6-month follow up with the 2nd intervention. There will be no difference in how subjects in the randomized intervention or second intervention will be monitored during the first eight weeks of the intervention. Subjects will not be paid for class attendance or evaluations during the 2nd intervention nor will they undergo MRS scanning. These data are exploratory.

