- (23) Subject has been treated a) with a scheduled dose of anti-anxiety agents (e.g., benzodiazepines) or sleeping aids (e.g. Ambien or sedative hypnotics) or b) with pain medication other than Non-Steroidal Anti-Inflammatory Drugs (NSAIDS) in the last one month except for procedure related pain management (e.g., dental procedures).
- (24) Has greater than three current criteria for Alcohol or Substance Use Disorder using DSM-V criteria.
- (25) Does not have a period of 48 hours of no alcohol use on TLFB to participate in scanning given the effects of alcohol consumption on the GABA.
- (26) Has a neurologic condition, such as a Traumatic Brain Injury (TBI) with a loss of consciousness of greater than 30 min, that in the opinion of the PI could compromise subject safety or the integrity of the study.
- (27) Has a medical condition that in the opinion of the PI could compromise subject safety or the integrity of the study.
- (28) Subject would not be expected to complete the study including scheduling issues.
- (29) Has an Axis-I diagnosis, other than depression except as listed, that in the opinion of the PI would interfere with the subject's participation in this study.
- (31) Has participated in another research study in the last 3 months that could affect the dependent variables.
- (32) Must have a period of 24 hours of no nicotine use on TLFB to participate in scanning or nicotine use as allowed by CSD&R Project Manager.
- (33) Subject does not agree to study procedures designed to protect against COVID-19 and the requirements of the virtual interventions.

3.3.2.7. Randomization: Group assignments will be conducted using permuted block randomization with varying block sizes. Block sizes will be multiples of the number of treatments and take the allocation ratio into account. For this study with a 1:1 randomization of 2 groups (yoga and walking), block sizes will be 2, 4, and 6. Randomization will be computer generated with each randomization assignment put on a card in numerically labeled envelopes that will be sealed. The envelopes will be opened in sequential order at the time of randomization by a member of the staff that is not blinded to group assignment. Subjects who want more time to think about participation can be randomized within 12 days of the last screening assessment, with the interventions starting within 7 days.

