4.5.2.6. Creation of a VHA Health Record: This study enrolls outpatients who are receiving a treatment intervention that may lead to physical or psychological adverse events and will be using the phlebotomy lab to collect blood for serum progesterone levels and pregnancy tests, which will be identified by the subjects VA identifiers. Because this study will request a Certificate of Confidentiality, a VHA health record will not be created. Instead a note entry will indicate that an individual has been enrolled in a research study, any details that would affect the subject's clinical care, and the name and contact information for the investigator conducting the study. Subject's informed consent forms and HIPPA authorization documents are not to be included in the health record. No pharmacologic agents are being given as part of the study, no research results being used for clinical care, the study interventions include a yoga or walking intervention, psychological forms and assessment instruments, electrocardiogram data, and imaging studies at the McLean Hospital.

4.5.2.7. Creation of a McLean Health Record: The McLean Hospital will create a medical record for the anatomic scan in which the subject will be identified by their name, date of birth, address, telephone number and social security number. This is a McLean Hospital policy and they will obtain the required HIPPA authorization for this record. This record will be kept separate from the subject's research information in which they will be identified by their study

identification number.

4.5.2.8. Enrollment: Participants are considered enrolled in the study when they give oral consent to the telephone interview. The Project Manager and research staff will usually do the telephone-

interview consent and telephone interview. Participants are considered enrolled in screening after they sign the written informed consent. The written informed consent can be obtained by research staff, however, the study MD needs to consent the subject with regards to the risks of the imaging part of the study prior to scanning. There are two lines on the IC for staff, such that the research staff can start the evaluation without the study M.D. Participants are considered randomized when they participate in their first intervention. This study uses walking as an active control. There is considerable literature to support the use of exercise as a treatment for depression, such that there is no deception in this study.

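### Printed block sizes of 2, 4 and 6, opened in sequence by unblinded staff whose other duties are not stated, leave the next assignment predictable well above chance and do not prevent selective entry

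*Protocol*

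**What the plan says.** Protocol section 3.3.2.7 specifies permuted blocks of varying size and names the sizes: "For this study with a 1:1 randomization of 2 groups (yoga and walking), block sizes will be 2, 4, and 6". On concealment it says: "Randomization will be computer generated with each randomization assignment put on a card in numerically labeled envelopes that will be sealed". The envelopes are "opened in sequential order at the time of randomization by a member of the staff that is not blinded" to group. Subjects who want time to consider "can be randomized within 12 days of the last screening assessment".

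Section 3.3.2.3 adds: "Prior to randomization, subjects will be asked their group of choice". The stated reason is that missing the preferred group could affect dropout.

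On roles:
- Section 3.3.2.4 gives the eligibility decision to the PI.
- Section 4.5.2.8 says of the telephone stage: "The Project Manager and research staff will usually do the telephone" consent and interview.
- Section 5.0 lists a 3/5-time PI, a full-time project manager and a half-time clinical staff member at the site.
- Section 3.3.2.8 says investigators do not know the assignment before randomization, and that HDRS and CAPS raters are blind.

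Section 2.2.q refers to stratifying on current PTSD, but section 3.3.2.7 mentions no strata. The SAP (D.17) does not discuss allocation.

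**The concern.** In a permuted-block list the running difference between arms returns to zero at the end of every block. Anyone who knows the earlier assignments can therefore guess that the arm currently behind comes next. They do not need to know where blocks start or end, so varying the block size gives little protection against this guess. The interventions are open and at one site, so past assignments are visible to the staff who run sessions and to whoever opens the envelopes.

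A guess does harm only if the person making it can also affect who enters, or when. The plan leaves room for that. Preference is known before allocation, entry can be delayed when a subject asks for time, and exclusions 26, 27 and 29 in section 3.3.2.6 rest on the PI's opinion. Exclusion 28 rests on whether the subject is likely to finish.

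The stake is comparability at entry. If Veterans who prefer yoga tended to enter when yoga was the likely next arm, the arms would differ in expectation. Participants are unblinded, and BDI-II, STAI, EIFI and PSQI are self-reports. Blinded rating after entry does not undo selection before it.

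**Working it through.** The documents give no predictability figure, so there is nothing to reproduce.

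**Inputs.** Two arms at 1:1 and blocks of 2, 4 and 6 (section 3.3.2.7). The probability of each size is not stated; equal probability is assumed and the extremes are shown. The number randomized is 84 in section 3.5.2 and 100 in sections 3.3.2.2 and 4.5.2.9; both were run.

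**Guessing rule.** Always guess the arm with fewer assignments so far, and toss a coin when they are level (the Blackwell-Hodges convergence guess). In a block of size 2m the expected number of correct guesses is

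E(m) = m + (4^m / C(2m, m) − 1) / 2.

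- Block of 2: 1 + (4/2 − 1)/2 = 1.500, or 75.0%.
- Block of 4: 2 + (16/6 − 1)/2 = 2.833, or 70.8%.
- Block of 6: 3 + (64/20 − 1)/2 = 4.100, or 68.3%.
- Equal mix: (1.500 + 2.833 + 4.100)/12 = 8.433/12 = 70.3%.

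Any mix of these sizes lies between 68.3% and 75.0%. Simulation under the equal mix gave 70.1% for 84 subjects and 70.2% for 100.

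**Strata.** With two PTSD strata (40% share assumed), a guesser who tracks each stratum is right 69.9% of the time. One who ignores the strata is right about 64%.

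**How much is known outright.** When the guesser knows the possible sizes but not the size of each block, about 4% of assignments are certain and about 59% can be predicted with probability 0.75 or more (simulation). If the size of each block were known, the certain share would be (1 + 4/3 + 3/2)/12 = 31.9%. Varying the sizes thus removes most of the certainty but leaves the average guess rate.

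**Would other sizes help?** Dropping the block of 2 gives (2.833 + 4.100)/10 = 69.3%. Blocks of 4, 6 and 8 give (2.833 + 4.100 + 5.329)/18 = 68.1%. Changing sizes alone does little.

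**A fair coin forced only when the arms differ by 4.** In the long run the absolute difference takes the values 0, 1, 2, 3, 4 with probabilities 1/8, 2/8, 2/8, 2/8, 1/8. Correct guesses are 7/8 × 1/2 + 1/8 × 1 = 56%. Assignments at the cap, 1/8 = 12.5% in the long run (11.6% by simulation), are certain to anyone who infers the rule.

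**Who could act on a guess.** The documents do not say who holds the envelopes, whether they are opaque, whether one is tied to a subject before opening, or whether the opener also enrols, schedules or asks the preference. With the three site posts in section 5.0, and the HDRS and CAPS raters kept blind, the opener could be the project manager, who shares telephone screening, or the PI, who decides eligibility. That is an inference; the text neither states nor excludes it.

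**The case against.** A reader might infer that 70% of assignments are known in advance and that the arms can be, or are being, selected. The documents do not support either. The 70% is an expected hit rate for someone who follows every earlier assignment, against 50% by chance. Selection also needs that person to control eligibility or order of entry, and no section says so. The envelopes are sealed and numbered, investigators are said not to know the assignment beforehand, and the telephone interview comes well before randomization. This stands, except that not knowing the coming assignment is different from not knowing the history that makes it predictable.

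The delay window is offered to subjects who want time to think, not to staff as a scheduling device. At the planned 25 randomizations a year, 12 days bring about 25 × 12/365 = 0.8 further entrants, so two candidates would not often be waiting together. This stands.

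The plan is not without protection. Preference is recorded, so it could enter the models under the baseline-imbalance rule in section 3.5.1 and SAP D.17, although neither names it; unmeasured prognosis could not. HDRS raters are blind, and GABA and RSA are analysed blind. Yoga and walking sessions run at the same time and assessments are on another floor (sections 3.3.2.12.1 and 5.0). These measures protect measurement after entry, not entry itself.

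A reader might also want a bias figure. If prognosis shifted by ±0.25 SD with the guess, the arm difference would be biased by 2 × 0.25 × (2 × 0.70 − 1) = 0.20 SD. That only restates the assumed shift, for which the documents give no basis.

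**Conclusion.** The concern holds as a gap in allocation concealment. The next assignment can be guessed correctly about 70% of the time by someone who tracks all earlier ones: 68% to 75% by block mix, about 64% if PTSD strata exist and are ignored, 50% by chance. The central figure assumes equally likely block sizes and full knowledge of past assignments. Because the envelope opener is not separated from those who screen, schedule or decide eligibility, selection is possible and not prevented. It is not shown, and no size of bias or error inflation follows from the documents. Closing the gap is a cheap improvement for the subjects still to be randomized; the point is not evidence against those already entered.

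**What to change.** For all remaining randomizations:

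- The study statistician generates and holds the list and loads it in the trial's existing REDCap system, replacing the envelopes.
- An assignment is released only after the PI has locked eligibility and the subject's preference has been recorded.
- The release is made by someone who does not enrol or schedule, where existing staffing allows.
- The statement that "block sizes will be 2, 4, and 6" is removed from the site protocol and kept with the statistician.

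A less predictable rule, such as the coin capped at a difference of 4, is optional. It lowers the average guess rate to about 56%, but makes about 12% of assignments certain at the cap and lets the arms end up to 4 apart (for example 44 and 40 of 84). Concealed release does not depend on it.

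The cost is a short amendment and REDCap set-up work.

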- (10) **Pittsburgh Sleep Quality Index (PSQI)** is a self-administered instrument that assesses 9 factors of sleep over a month period, providing a composite score, with higher scores indicating poorer sleep quality.(71)
- (11) **Timeline Follow Back (TLFB)** will be used to assess alcohol consumption for three months prior to screening.(72) A format similar to the TLFB will be used for nicotine consumption.
- (12) **Brief Pain Inventory**, an eleven point Likert Scale of pain intensity will be used to assess pain over the last 24 hours.
- (13) **Stroop Color-Word Test** is a selective attention and inhibitory cognitive control task.(74)

Individual Time Line	Table 3: Individual Time Line and Collection of Dependent Variables		
	Aim 1	Aim2	Aim 3
Individual Time Line	Depression Scales	Mood Scales	GABA RSA
Telephone Screen			
Screening Session	HDRS/BDI-II 1		
3T Brain Scan			
MRS Imaging Session 1			
Pre Scan 1 Measures	HDRS/BDI-II 2	EIFI & STAI 1	RSA 1
MRS Scan 1(Baseline)			GABA 1
Randomization			
Week 4			
Pre-Week 4 Evaluation		EIFI & STAI 2	RSA 2
Week 4 Intervention			
Post-Week 4 Evaluation	HDRS/BDI-II 3	EIFI & STAI 3	RSA 3
Week 5-7 Intervention			
Week 8			
Pre-Week 8 Evaluation		EIFI & STAI 4	RSA 4
Week 8 Intervention			
Post-Week 8 Evaluation	HDRS/BDI-II 4	EIFI & STAI 5	RSA 5
Week9-11 Intervention			
Week 12			
Pre-Week 12 Evaluation		EIFI & STAI 6	RSA 6
Week 12 Intervention			
Post-Week 12 Evaluation	HDRS/BDI-II 5	EIFI & STAI 7	RSA 7
MRS Imaging Session 2			
Pre Scan 2 Evaluation	HDRS/BDI-II 6	EIFI & STAI 8	RSA 8
Scan 2			GABA 2
Interscan Intervention			
Pre-Scan 3 Evaluation		EIFI & STAI 9	RSA 9
Scan 3			GABA 3
Follow-Up 2 month	HDRS/BDI-II 6	EIFI & STAI 10	
Follow-Up 6 month	HDRS/BDI-II 6	EIFI & STAI 11	

(14) **Digit Symbol Substitution Test (DSST)** is one of the frequently used tests to measure psychomotor slowing, and is clinically sensitive because it makes demands on several processes, including perception, working memory, sustained attention and visuomotor co-ordination (Wechsler 1997).

(15) **Child Trauma Questionnaire (CTQ)** is a self-report measure of childhood trauma. (73) This scale will be given during the Week 4 evaluation at the end of the session.

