for certified yoga instructors with Iyengar training who have at least 5 years teaching experience. Instruction in coherent breathing is necessary because the positive effects on sympatho-vagal balance depend not only on the respiratory rate, but also on degree of effort, depth, and muscle relaxation while breathing. Without proper instruction, some inhale too rapidly, overfill their lungs, exhale too forcefully, overuse abdominal muscles, or breathe paradoxically (contracting abdominal muscles while inhaling). Any of these errors could increase sympathetic activation, interfere with parasympathetic activation or even cause hyperventilation. (16) Instructors are needed to observe subject breathing and to monitor and provide corrective feedback.

The COVID-19 pandemic has resulted in all of the yoga instructors providing yoga classes virtually. In order to support social distancing the yoga interventions will be provided virtually through a platform approved by the ISSO officer, such as VA Video Connect. The yoga instructors will teach all yoga interventions virtually. The subjects will be required to attend the randomization, and weeks 4, 8, and 12 interventions at the VABHCS so that equipment can be provided or collect and pre and post intervention data can be collected.

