(iii) VA tours of duty or time allocations: The PI's 3/5th VA appointment is equivalent to 24 hours a week plus a 30 minute meal break for period of work over 4 hours. This study will be run using the same structure that has worked for the civilian version of this study. In order to provide intervention times such that individual who are and are not employed can participate in the study, the interventions will be conducted from 8 am to 9:30 am and from 5 pm to 6:30 pm on Monday and Wednesday, the days of the intervention can be changed or additional sessions added as needed. The week 4, 8 and 12

evaluations that take place before and after the interventions and take around 45 minutes. To accommodate this schedule, [name] VA tour of duty will be from 7:30 am to 8:00 pm on Monday and Wednesday which includes a 30 minute meal break. After subtracting 30 minutes for lunch each day this results in two 12-hour tours, 24 hours or 3/5th time.

(iv) Issues related to data ownership: All data collected at the McLean Hospital will be collected under a contract which will state that the data belong to the VABHCS. All data analyzed by [name] belongs to the VABHCS. Research information protection and data security requirements. The protocol approved by Veterans Administration Central Office (VACO) included permission for [name] to be off site to oversee the collection and analysis of data at the McLean Hospital and for [name], [name], the study physicist to have access to a Limited Data Set. HIPPA identifiers will remain within the REDCap database, the VA Medical Health Record and the McLean Medical Health Record.

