Hypothesis 4. a. Exploratory Concurrent Antidepressants: The yoga group but not the walking group will have a decrease in depressive symptoms regardless of antidepressant treatment at the beginning of the study.

Hypothesis 4. b. Exploratory PTSD Symptoms: If PTSD symptoms are present at screening, there will be a greater decrease in PTSD symptoms in the yoga compared to the walking group as measured by CAPS and PCL-C.

Hypothesis 4. c. Resting State Connectivity will increase over the course of the study with greater increases in the yoga group.

Hypothesis 4. d. Executive Function will increase over the study as measured by the Stroop, Digit Symbol test and fMRI activation.

3.5.2. Power Analysis for Depressive symptoms and Mood Scales: Based on the power analyses below, in order to achieve adequate power for all analyses, n=70 subjects, n=35 in the yoga and n=35 in the walking intervention must complete the interventions. Using Study 4 data in subjects with MDD in the LDG, the repeated measures ANOVA for EIFI scores from screening to the completion of the intervention did not reach statistical significance in the group of n=15 (baseline: 3.1 ± 2.2 and week-12: 3.9 ± 2.7 , $F_{1,13} = 1.097$, $p = 0.31$), a post hoc power analysis was conducted, which determined that the achieved effect size was $f = .281$, with 52% power. Based on this same effect size, an a priori power calculation was conducted, which determined that **n=35** subjects would be needed to detect significant differences for BDI-II, STAI, and EIFI scores from screening to the completion of the intervention, with effect size $f = .281$, with $< = .02$ to account for multiple comparisons, and 81% power. As the power analysis for the EIFI requires the largest number of subjects (n=70), which will be used to determine sample size. In order for 70 subjects to complete the intervention, assuming a 20% drop out, 84 subjects will be randomized.

3.5.3. Power Analysis for GABA: Consistent with our analytic plan for the longitudinal questions at-hand, we can compute the statistical power for Hypothesis II an analysis sample of **n=26** subjects in each of the study groups using the mixed linear model analogue of repeated measures analysis-of-

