4.5.2.9. Recruitment: This proposal contains a randomized controlled trial in a clinical population in which 70 subjects will complete the protocol and around 420 will have a telephone-screening interview. Although this efficacy trial is not large or multi-centered, it is considered a Phase 2 trial due to the previous trial in healthy controls (Study 2) and the dosing trial in depressed subjects (Study4).

Sample size calculations, based on power analyses, require the following number of completers equally divided between the yoga and walking groups to test the hypotheses for each dependent variable: n=70 completers to test Aim 1: Depressive Symptoms and Mood Scale, n=56 to test Aim 2: GABA changes and n=68 to test Aim 3: RSA changes. To meet the criteria for each Aim/Dependent Variable 70 subjects will complete the intervention with 56 having usable MRS data. Using data from Study 4, with consideration of changes in inclusion and exclusion criteria and research setting, the following recruitment schedule will be required during a 5 year study period, which will include over 4 years of recruitment and treatment. The required total recruitment and annual requirements at each stage are as follows: telephone screen 420 total or 105/year; screening interview 173 total or 43/year; randomization 100 total or 25/year; and completers 70 total or 18/year over a 4 year recruitment period.

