A Randomized Control Trial Treating Depression With Yoga and Coherent Breathing Versus Walking in Veterans

NCT03489122

Document Date: 3-20-2017

D.17. Data Management and Analysis Plan: The Data Coordinating Center at the Boston University School of Public Health will provide data management, including the development and maintenance of a REDCap database and the creation of a final database that will be sent to [name] for statistical analysis, using SPSS 23.0. Descriptive statistics will be generated for baseline data and distributions between the yoga intervention and walking intervention will be compared using two-sample t-tests and chi-square or Fisher's exact tests to assess effectiveness of randomization. Descriptive statistics include means and standard deviations for continuous variables and group sizes and proportions for categorical variables. All analyses will be performed at the $\alpha = 0.05$ level of significance. Should groups have unequal distributions at baseline, relevant variables will be incorporated in subsequent linear models that will be used to examine intervention efficacy. In order to address the study aims of assessing the relative longitudinal change in dependent variables between yoga intervention and walking intervention groups over time, data will be collected at four time points, pre-randomization, and at weeks 4, 8, and 12. Mixed linear model analyses will be performed focusing on the group x time interaction for the primary effects to be statistically modeled. These analyses will allow for inclusion of data at differing numbers of time points per subject if needed. We will examine different within-subject correlation structures for our interaction model and determine the optimal structure by comparing Akaike information criteria (AIC) values. The correlation structure that yields the lowest AIC will be adopted. Subjects who change antidepressant medications during the study will be included in intent to treat analysis, but will be co-varied for medication changes. Potential cohort effects will be statistically addressed by controlling for group profiles, including group size, breakdown by sex of attendees, instructor, group parameters such as individual or group sessions, and group cohesion/overlap.

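### The plan provides no week 4, 8 or 12 HDRS for randomized participants who stop attending sessions, so the week-12 comparison may estimate the effect had everyone continued

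*Protocol*

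**What the plan says.** **Timing of the ratings.** In Table 3 (protocol 3.3.2.1) the treatment-week HDRS/BDI-II appear only in rows such as "Post-Week 12 Evaluation", each placed directly after that week's intervention row. Section 3.4.3.7(iii) describes the week 4, 8 and 12 assessments as "evaluations that take place before and after the interventions". Section 3.3.2.11, in its paragraph on virtual classes, has participants attend on site the "weeks 4, 8, and 12 interventions at the VABHCS so that equipment can be provided or collect and pre and post intervention data can be" obtained. Section 3.3.2.12 asks the walking arm for the same number of on-site visits.

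Other places tie the assessments to the week rather than to the session. These are section 3.2 and the text following the instrument list (HDRS by week), section 3.3.2.14 (in-person staff evaluations at those weeks), and sections 3.3.2.10 and 4.7 (evaluations paid separately from sessions). None of them says what happens to the rating once a participant no longer attends.

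**Expected losses.** Section 3.5.2: "In order for 70 subjects to complete the intervention, assuming a 20% drop out, 84 subjects will be randomized". Section 4.5.2.9: "randomization 100 total or 25/year; and completers 70 total or 18/year over a 4 year recruitment period". Section 3.3.2.2 also has 100 randomized, but with "completers=68 total or 18/year". Sections 3.3.2.2 and 4.5.2.9 count completers as the number needed to test each aim.

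**Analysis.** SAP D.17, and protocol 3.5.1 in the same terms, uses a mixed linear model of group by time over four time points (pre-randomization and weeks 4, 8 and 12). On incomplete data it says only: "These analyses will allow for inclusion of data at differing numbers of time points per subject if needed". It states no missing-data assumption, no sensitivity analysis and no rule for participants who stop the intervention. Intent to treat is mentioned once, for participants who change antidepressants.

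**The concern.** Staff following the protocol as written have an instruction to rate a participant who comes to the week 4, 8 or 12 session, and none for one who has stopped coming. If no rating is taken, the primary outcome is missing for a reason tied to treatment itself, and readings that were never collected cannot be recovered in the analysis.

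What is at stake is which effect the week-12 HDRS comparison estimates. Without readings after stopping, it moves from the effect in all randomized Veterans towards the effect had everyone kept attending. A larger sample does not remove that gap. Stopping may also differ by arm. Yoga sessions last 90 minutes against 60 for walking, yoga homework lasts 30 minutes against 15, and section 3.3.2.3 recognises that not getting the preferred arm could affect dropout.

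**Working it through.** **1. The plan's own figures.** The 84 in section 3.5.2 is reproduced by 70 × 1.20 = 84. (Dividing instead, 70 / 0.80 = 87.5, gives 88.) Implied all-cause non-completion:

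- 84 to 70: 14/84 = 16.7%
- stated in section 3.5.2: 20%
- 100 to 70 (section 4.5.2.9): 30/100 = 30%
- 100 to 68 (section 3.3.2.2): 32/100 = 32%

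Section 4.5.2.4 counts a participant as randomized on attending a first session, so these losses are people who started and did not complete.

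**2. Other HDRS readings.** Table 3 lists HDRS before Scan 2, but the text list for the imaging sessions has BDI-II and not HDRS, and section 3.3.2.17 lets the study go on without imaging. The 2- and 6-month calls assess depression and are not limited to completers, but they lie outside the four modelled time points.

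**3. General form.** Let Δ be the week-12 yoga advantage if all attend, d_Y and d_W the shares stopping in each arm, and L_Y and L_W the HDRS benefit lost by week 12 among stoppers in each arm. Then:

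- effect in all randomized = Δ − d_Y·L_Y + d_W·L_W
- effect estimated with no readings after stopping ≈ Δ
- error = d_Y·L_Y − d_W·L_W

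With the same stopping share d in both arms, and stoppers keeping a fraction r of the yoga-walking difference, the effect in all randomized is Δ × (1 − d(1 − r)), and the overstatement is 1 / (1 − d(1 − r)) − 1.

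**4. Numbers.** The documents give neither Δ for HDRS nor r. Assume Δ = 3 points. The percentages do not depend on Δ.

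| d | r = 0: effect, overstatement | r = 0.5: effect, overstatement | r = 1 |
|---|---|---|---|
| 16.7% | 2.50, 20% | 2.75, 9% | 3.00, 0% |
| 20% | 2.40, 25% | 2.70, 11% | 3.00, 0% |
| 30% | 2.10, 43% | 2.55, 18% | 3.00, 0% |
| 32% | 2.04, 47% | 2.52, 19% | 3.00, 0% |

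**5. Does the model return Δ?** Two large simulations of the likelihood estimate say so, both with within-subject correlation 0.6, full loss of the difference and no readings after stopping.

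- Δ = 3 points, SD 6, stopping after week 4: estimates 2.99, 2.99 and 3.00 at 16.7%, 20% and 30% stopping, against 2.49, 2.39 and 2.10 in all randomized.
- Δ = 0.70 SD, stopping dependent on the week-4 score, half of the stoppers keeping a week-8 reading: estimates 0.70, 0.70 and 0.69 SD, against 0.58, 0.56 and 0.48 SD.

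**6. Direction.** With Δ = 3 and d = 20% in both arms:

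- Both arms' stoppers lose 2 points: error = 0.2 × 2 − 0.2 × 2 = 0.
- Yoga stoppers lose 1 and walking stoppers lose 2: the effect in all randomized is 3 − 0.2 + 0.4 = 3.2, so an estimate of 3.0 understates it.

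**The case against.** The strongest reply is that the plan is silent rather than restrictive. Several sections schedule the evaluations by week and pay for them separately, and Table 3 may only show the usual order of a visit day. That stands. A reader might infer that stoppers are refused the HDRS or cannot have a week-12 primary outcome; the documents do not say so. What remains is that no section provides the rating.

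Second, the 17% to 32% covers every reason for not completing, including withdrawal on safety grounds, leaving for other treatment, and people who can no longer be reached. That also stands. It should not be read as the share who merely stop attending but remain reachable, for which the documents give no figure. The pilot dosing study (section 2.2.h) kept 30 of 32, missed classes can be made up, and there is a retention plan, so actual losses may be smaller than budgeted.

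Third, a mixed model on all available visits is standard, and the protocol calls this an efficacy trial. An effect under continued attendance is a legitimate target, but the plan does not name it. Collecting the readings leaves either analysis open.

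Fourth, the SAP does not describe the primary analysis as intent to treat for people who stop. It uses the term only for antidepressant changers and defines no analysis set, so this point rests on the gap and not on a broken promise.

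**Conclusion.** The point holds as a gap in outcome collection, with a consequence that is conditional. If ratings end when sessions end, the model keeps the readings already taken and implicitly extrapolates later visits from same-arm participants who stayed. The week-12 contrast then approximates the effect had all continued.

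The range, from no error to a 43% overstatement at 30% stopping (47% at 32%), rests on three assumptions: all non-completers lack later ratings, stopping is equal between arms, and stoppers keep between all and none of the yoga-walking difference. The upper figures are the full-loss case and not a forecast.

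A reader might infer that the yoga effect is bound to be overstated, or that the error vanishes only if stopping has no effect on later HDRS. Neither follows. Walking is an active control, so its stoppers can lose benefit too. With equal stopping, equal loss in both arms gives no error, and greater loss in walking reverses it. The protocol does, however, treat attendance as the dose needed for symptom reduction (section 3.3.2.10), and section 2.2.h reports BDI-II falling as yoga minutes rise. The plan therefore cannot simply take the no-error case for granted. The sponsor should make the change, because the missing readings cannot be replaced later.

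**What to change.** - **Protocol Table 3 and 3.3.2.11-12:** schedule the week 4, 8 and 12 HDRS and BDI-II by weeks since randomization for every randomized participant who has not withdrawn consent, whether or not a session is attended. Where the participant no longer attends, use telephone or video with the existing blinded raters. Telephone follow-up of depression is already planned (section 3.2), and section 4.5.2.3 already allows much of screening by phone or video.
- **SAP D.17 and protocol 3.5.1:** include these readings in the primary mixed model under assigned arm.

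This concerns outcome ratings only and alters no treatment, withdrawal or safety rule.

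The cost is wording in both documents and some extra calls. At most three ratings for 14 to 32 non-completers is 42 to 96 ratings, and in practice fewer, because late stoppers already have earlier readings and some people will be unreachable. The downsides are a mix of in-person and remote ratings, and that some stoppers will decline, so the gap would shrink rather than close.
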